TAT	Thrombin-antithrombin
TB	Tuberculosis
TCAE	Terminology Criteria for Adverse Events
Tid	Three times daily
TNF	Tumor Necrosis Factor
ULN	Upper Limit of Normal
UNOS	United Network of Organ Sharing
WHO	World Health Organization
y.o.	Years old

Study Definitions

Full graft function: Islet transplant recipients will be considered to have full islet graft function if they are insulin independent (as defined below).

Graft failure: Islet allograft failure will be defined as absence of insulin production by transplanted islets, as evidenced by c-peptide < 0.3 ng/mL. This will be determined by (1) c-peptide < 0.3 ng/mL on random testing, followed by (2) c-peptide < 0.3 ng/mL at baseline, and at 60 and 90 minutes after MMTT. Participants with graft failure do not need to complete the day 75 metabolic assessments.

Insulin-independent: Islet transplant recipients will be considered insulin-independent with full islet graft function if they are able to titrate off insulin therapy for at least 1 week and all of the following criteria are met:

- One HbA1c level, one fasting serum glucose level, and a Mixed Meal Tolerance Test are documented within the visit window (e.g. 70-80 days at Day 75) and 7 consecutive days of blood sugar and insulin readings are documented within ± 7 days of the visit window (e.g. 63-87 days at Day 75);
- HbA1c $\leq 6.5\%$ or a $\geq 2.5\%$ decrease from baseline (within 91 days prior to transplant);
- Fasting capillary glucose level should not exceed 140 mg/dL more than three times in 7 consecutive days (fasting is defined as 1st blood sugar reading of the day not noted as post-prandial or bedtime);
- Post-prandial serum glucose ≤ 180 mg/dL at 90 minutes during the MMTT;
- Fasting serum glucose level ≤ 126 mg/dL; if the fasting serum glucose level is > 126 mg/dL, it must be confirmed in an additional one out of two measurements;
- At least one MMTT fasting or stimulated c-peptide ≥ 0.5 ng/mL.

Insulin dependent: Islet transplant recipients who do not meet the criteria for insulin independence will be considered insulin-dependent.

Intensive diabetes management: Self-monitoring of glucose values no less than a mean of three times each day averaged over each week and by the administration of three or more insulin injections each day or insulin pump therapy.

Partial graft function: Islet transplant recipients who do not meet criteria for insulin independence, but have either a basal or stimulated c-peptide level ≥ 0.3 ng/mL (0.1 nmol/L).

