4.1 Study Endpoints

Since our primary thesis is that GLASSIA will increase islet engraftment in the early perioperative period our primary endpoint for which the study is powered is a comparison of insulin independence rates of GLASSIA treated versus control patients at day 75 post transplant. We are fortunate to have permission to utilize data from the CIT-06 trial which will allow a large number of control patients. Since our proposed trial was directly derived from CIT-06 in terms of entry criteria, treatment regimen and post transplant monitoring except for treatment with GLASSIA and related mechanistic studies, these cohorts provide us a highly relevant comparator and allow us to enroll more GLASSIA treated patients than if a randomized trial. This increases the power of the trial making it likely that we will be able to detect differences between treated and control groups should GLASSIA exert the hypothesized benefit to engraftment.

For our primary mechanistic assessment to measure engrafted functional islet mass we will rely on the frequently sampled intravenous glucose tolerance test (FSIGT) from which an AUC for insulin secretion correlates with islet mass. Each of the 24 CIT-06 patients had this test performed at day 75. Of note, we had previously considered use of a glucose potentiated arginine stimulation test for this purpose. However, no CIT-06 patients had this test performed¹³¹⁻¹³².

Because the assessment of islet graft function is dependent on complex physiologic relationships between the graft and its recipient, no single test adequately addresses the metabolic impact of the transplant. Therefore, HbA1c and the number of episodes of severe hypoglycemia will be used as clinically relevant measures of islet graft function for secondary endpoints, and additional stimulatory tests of islet graft function utilizing MMTT, glucose, and the CPGCR will be used to assess secondary endpoints. Also, the effect of islet graft function on glycemic control (HbA1c), glycemic lability (MAGE and LI), hypoglycemia (Clarke and HYPO scores), glucose variability (CGMS®), cardiovascular impact, and renal impact will be assessed as additional secondary endpoints¹³²⁻¹³⁶. Each of these were collected in CIT-06 patients and will add to the robustness of our comparison of the metabolic outcome between GLASSIA treated and control CIT-06 subjects.

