5.8.2 Modification of Standard Immunosuppression

ISLETS ARE UNSUITABLE

Should an islet product become unsuitable for transplantation subsequent to induction immunosuppression, the subject will remain on maintenance therapy required for their renal transplant. This will provide sufficient time for organ procurement, islet isolation, and infusion of an islet product without any additional induction treatment to the recipient. An emergency request will be placed through UNOS that the next available pancreas for islet transplantation is directed to the selected manufacturing site. When an organ becomes available, investigators should defer to the MOP to determine the amount and type of induction immunosuppression that will be administered at the time of islet transplant.

GRAFT FAILURE

Subjects who experience islet graft failure will be maintained on their current immunosuppressive regimen for their renal graft as long as a subsequent islet transplant is possible. If/when it is determined that a subject will not receive a subsequent islet transplant, the subject will move to the reduced follow-up schedule.

ALLERGIC REACTION TO ATG

If a subject demonstrates an allergic reaction to thymoglobulin that results in cancellation of the initial transplant and the investigators feel that future use of the drug in the subject is contraindicated, the steps outlined should be followed. Once another organ becomes available, the subject will receive the alternate induction immunosuppressive regimen outlined in this protocol.

INTOLERANCE OF PROTOCOL MEDICATIONS

In the event that protocol-regulated concomitant medications are not tolerated, the subject will continue taking the immunosuppressive therapy in order to protect the islet and renal grafts. In the event that the immunosuppression regimen is not tolerated, the site PI may elect to prescribe an alternative immunosuppression regimen. The intent would be for the alternative regimen to be temporary in nature.

where possible and any such decision made with the primary interest of maintaining the function of the renal allograft. Any non-protocol directed study treatment modification that the site PI determines is necessary should be reported as a protocol deviation.

RABBIT ANTI-THYMOCYTE GLOBULIN-INDUCED ANAPHYLAXIS

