10. STATISTICAL CONSIDERATIONS AND ANALYTICAL PLAN

10.1 Study Endpoint Assessment

10.1.1 Primary Endpoint

Since our primary thesis is that GLASSIA will increase islet engraftment in the early perioperative period our primary endpoint for which the study is powered is a mechanistic assessment of the functional islet mass early (day 75) post transplant. We will rely on the frequently sampled intravenous glucose tolerance test (FSIGT) from which an AUC for insulin secretion correlates with islet mass for our primary mechanistic assessment of functional islet mass. Data from the CIT06 trial, which performed this test on all patients at day 75, will serve as the control. Such controls increase the power of the trial making it likely that we will be able to detect differences between treated and control groups should GLASSIA exert the hypothesized benefit to engraftment.

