Most of the secondary endpoints are measured before transplant, at day 75 (A1c, MMT, FSIGT, MAGE, c-peptide and Beta score) and at one year post-initial transplant (HbA1c, fasting and 90 minute MMTT, c-peptide, glucose, and c-peptide glucose creatinine ratio, MAGE, HYPO, Clarke survey, and Beta score). We will compare these markers with those in the CIT-06 controls using student's t-test, nonparametric test (e.g., Mann-Whitney U test, Wilcoxon signed rank test), or chi-square test when appropriate. A pre-post analysis will be used for these variables. For continuous variables that are normally distributed or that can be transformed to a normal distribution, we will compute an appropriate estimate and 95% confidence interval for the mean change and a paired t-test for testing that the mean change is zero. If an appropriate normalizing transform cannot be identified then a signed-rank test will be used to test for a significant change. Similarly, a McNemar test will be used to test for a significant change for dichotomous outcome variables.

For those continuous secondary endpoints that are only observable after transplantation or for whom

change from baseline are not meaningful we will compute estimates of the mean and 95% confidence intervals. Similarly, for binary endpoints we will compute the observed rates and exact 95% confidence intervals. Levels of these markers will be compared with those in the CIT-06 controls using student's t-test or nonparametric test (e.g., Mann-Whitney U test) when appropriate.

Regression models for continuous longitudinal data (mixed models) will be used to describe the profiles of change over time for each of the response variables where measurements are repeated over time. Similar models will be used to model dichotomous variables over time.

Survival analysis models will be used to compare time to becoming insulin dependent and to identify risk factors through Kaplan-Meier estimates and Cox regression models.

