10.1.3 Exploratory Endpoints

Exploring novel approaches to monitoring islet graft injury will serve as the basis for hypotheses generation in future trials. We will calculate descriptive statistics for the safety and efficacy of the new approaches. Adverse events rates will be tabulated and 95% confidence intervals (CI) will be calculated. We will calculate the mean, median, minimum, maximum, inter-quartile ranges, and 95% CI of loss of engrafted islets estimated by early post infusion release of insulin specific DNA, TAT and C3a. Success rate and 95% CI will be estimated.

Other secondary and exploratory endpoints include relative functional engrafted islet mass, the proportion achieving insulin independence, the proportion achieving HbA1c \leq 6.5% and an absence of severe hypoglycemic events, the proportion achieving HbA1c $<$ 7.0%, reduction in HbA1c of at least 1 point, the change in Clarke score, c-peptide, Glycemic lability index (LI), glucose and glucose variability. These endpoints will also be analyzed using descriptive statistics.

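### The day-75 FSIGT comparison can lose the GLASSIA graft failures, because they may skip the test and no value is assigned to them, while all 24 CIT-06 controls were tested

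*Combined protocol and SAP*

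**What the plan says.** The Study Definitions define graft failure as absent insulin production (c-peptide below 0.3 ng/mL on random testing, then at baseline and at 60 and 90 minutes of an MMTT). They add: "Participants with graft failure do not need to complete the day 75 metabolic assessments".

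Section 5.8.2 says that once a failed subject is known not to be getting another islet transplant, "the subject will move to the reduced follow-up schedule". Appendix 2, which sets out that schedule, has no FSIGT at any visit.

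For the controls, section 4.1 says of FSIGT: "Each of the 24 CIT-06 patients had this test performed at day 75". Section 10.1.1 repeats that CIT-06 is the trial "which performed this test on all patients at day 75, will serve as the control".

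Section 10.1.2 lists the secondary endpoints measured "at day 75 (A1c, MMT, FSIGT, MAGE, c-peptide and Beta score") and continues: "We will compare these markers with those in the CIT-06 controls using" a t-test, a nonparametric test or a chi-square test. Section 10.1.3 adds: "Other secondary and exploratory endpoints include relative functional engrafted islet mass" among others, and "These endpoints will also be analyzed using descriptive statistics".

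Neither section says what value, rank or missing-data rule applies to a failed graft that was not tested. The intent-to-treat statements in 5.8.3 and 6.1 cover data that were collected. They supply nothing for a test that was not done.

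**The concern.** The reason for the missing value is the outcome itself. FSIGT AUC stands for engrafted islet mass, and the subjects who are excused are by definition those with almost no insulin output. If they skip the test and the analysis uses available values, the bottom of the GLASSIA distribution is cut off and the control distribution is left whole.

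The controls are external and the trial is open-label and non-randomized (7.8.1), so nothing in the design offsets unequal missingness. The comparison also bears directly on the primary objective in 2.1, which is that AAT increases functional engrafted islet mass. A difference in favour of GLASSIA could then arise partly from who was measured. The descriptive summaries in 10.1.3 are exposed in the same way as the tests.

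**Working it through.** **The plan's own figures.** There is no power, SD or effect size for FSIGT, and Table 9 does not include it. The power in Table 7 concerns insulin independence and reproduces with an exact binomial rule of at least 8 of 20:

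- P(X ≥ 8 | n = 20, p = 0.167) = 0.0114. A cutoff of 7 would give 0.0375, which is above 0.025.
- P(X ≥ 8 | n = 20, p = 0.50) = 0.868, against the stated 87%.

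That result does not depend on FSIGT. The Study Definitions class anyone who does not meet the independence criteria as insulin-dependent, so failures are counted there.

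**Does the waiver cover FSIGT?** For: 10.1.2 lists FSIGT with MMTT, MAGE and c-peptide as day-75 measures. Appendix 1 puts it directly after MMTT and before CGMS, outside the block of mechanistic assays. Against: section 9.1 on metabolic testing itemises its tests without FSIGT, and 4.1 and 10.1.1 present FSIGT as a mechanistic assessment. Coverage is plausible but not stated.

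**Effect on the mean.** Assume failures have an AUC near 0. Omitting k of 20 multiplies the GLASSIA mean by 20/(20 − k):

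| k omitted | Factor | Inflation |
|---|---|---|
| 1 | 20/19 | 5% |
| 2 | 20/18 | 11% |
| 3 | 20/17 | 18% |
| 4 | 20/16 | 25% |

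**Effect on the test.** Inputs from the documents: 20 GLASSIA subjects, 24 controls, and a one-sided 2.5% level borrowed from 10.3.1. Assumptions: no drug effect, the same lognormal AUC distribution in both cohorts (CV 0.5), failures scored 0, and failure rate f. The test is Mann-Whitney with tie and continuity corrections, with 40,000 simulated trials per setting. Each cell is the share of trials that declare GLASSIA better.

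| f | Equal f, all GLASSIA failures skip | Equal f, each skips with probability one half | f in GLASSIA only, all skip | Equal f, all kept at lowest rank |
|---|---|---|---|---|
| 5% | 4.2% | 3.4% | 2.4% | 2.5% |
| 10% | 7.2% | 4.2% | 2.5% | 2.3% |
| 15% | 11.1% | 5.3% | 2.5% | 2.2% |
| 20% | 17.1% | 6.5% | 2.4% | 2.5% |

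If GLASSIA is truly worse (20% failures against 10%), omitting its failures declares it better in 6.7% of trials, against 0.6% when they are kept at the lowest rank.

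The t-test, which 10.1.2 also allows, moves the same way. At equal f = 10% with all failures skipping it gives 5.7% to 9.4% for an AUC CV of 1.0 down to 0.4.

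**The case against.** The strongest reply is that the larger error rates need several things together, none of them documented: CIT-06 patients with graft failure who were nevertheless tested, GLASSIA failures at similar rates, and GLASSIA failures who all skip. The waiver permits skipping and does not require it. Section 4.1 describes this trial as derived from CIT-06 in its post-transplant monitoring. If CIT-06 had the same waiver, which is not stated, 24 of 24 tested would suggest few or no control failures by day 75, and the false-positive rate would then stay near 2.5%. All of this stands, and it is why the size has to be given as a range with its conditions.

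It is also fair that failures remain visible elsewhere. They count against GLASSIA on the primary endpoint. Four consecutive subjects with c-peptide below 0.3 ng/mL at day 75, or repeated primary non-function, trigger suspension under 6.2.1 and 6.2.2. FSIGT is a secondary endpoint in 4.1.2, and 10.1.2 promises qualifiers. Those qualifiers, however, concern multiple endpoints and not selectively missing values.

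The descriptive analysis in 10.1.3 need not contradict 10.1.2, because its wording can be read as an addition to the tests. That does not help, since means computed without the failures are inflated too.

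What the reply does not supply is a rule for a failed graft that was not tested.

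**Conclusion.** The point holds in conditional form. As written, the plan allows the day-75 islet-mass comparison to omit the lowest GLASSIA values while the control values are complete, and any resulting bias favours GLASSIA. The size rests on assumed failure rates: 5% to 25% on the mean for 1 to 4 omitted failures, a false-positive rate of about 4% to 17% if all skip or about 3% to 7% if half skip, and no inflation if CIT-06 had no failures. In that last case the cost is that an excess of failures on GLASSIA does not show in this comparison.

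A reader might infer that the trial's main result is at risk, or that an error rate as high as 17% is to be expected. The documents support neither. The primary endpoint counts failures as insulin-dependent, and no failure rate is given for either cohort. Section 10.1.1 does call day-75 functional islet mass the endpoint for which the study is powered, but that conflicts with 4.1.1 and 10.3.1. It is a separate defect and should not raise the weight of this one. Nor do the documents say that failures must be excluded, or that the waiver certainly covers FSIGT. A separate SAP is mentioned in 10.2.4 and 10.5, and nothing in the combined document fills the gap.

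**What to change.** In 10.1.2:

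- State that subjects who meet the graft-failure definition stay in the day-75 FSIGT comparison, in both cohorts.
- Use the measured FSIGT value where there is one. Where the test was not done because of graft failure, assign the lowest rank, with AUC 0 in a sensitivity analysis.
- Name the rank test as the test for this endpoint, and report the number of failures and of untested subjects per cohort.
- Give one rule, the same in both cohorts, for subjects with partial function who are retransplanted before day 75, and report their number. Section 7.6.1 allows a second transplant from day 30 ± 3 and 7.5 then resets the assessment clock, so these subjects may have no first-transplant day-75 value and are not graft failures. One option is to use their last status before retransplant in a sensitivity analysis.

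In 10.1.3, state that the descriptive summaries use the same set of subjects. In the Study Definitions, say whether the waiver includes FSIGT.

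The cost is a few sentences and no new visits or tests. Graft-failure and early-retransplant status for CIT-06 must be read from the data that the sponsor has permission to use. The drawback is that an assigned rank is cruder than a measured value.

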1. BACKGROUND AND RATIONALE

1.1 Background

Of the nearly 15 million Americans afflicted with diabetes, almost 2 million have the Type 1 form of the disease in which insulin-producing islet β (beta) cells are destroyed by autoimmunity. This β cell selective attack disrupts normal glucose homeostasis and renders the host dependent on exogenous insulin administration for effective glucose utilization. While administration of daily exogenous insulin is a life-saving therapy, patients are still at risk of a spectrum of microvascular and macrovascular pathologies due to the imperfect glycemic control provided by even the most modern insulin therapy regimens². The resulting morbidity and mortality from complications of the disease represents a significant health care burden to the US and other countries and accounts for a large percentage of US health care related expenditures³.

Convincing data exist to document the close association of the degree of glycemic control with the risk of developing diabetes-related complications. In the seminal Diabetes Control and Complications Trial (DCCT), an IIT regimen improved HbA1c levels versus conventionally treated patients (mean 9.1 vs. 7.2% at the trials end) and progression of retinopathy, neuropathy, and nephropathy were tightly linked to glycemic control⁴⁻⁶. In fact, in general, a 30- 35% reduction in microvascular complications was achieved by an average of 1% reduction in HbA1c. Moreover, there was no threshold HbA1c below which a benefit was not observed, nor was there a minimal reduction in a high HbA1c that was not associated with benefit. Some patients receiving IIT also demonstrated sustained endogenous insulin responses as measured by induced c-peptide⁵. Unfortunately, the attempt at rigorous control was associated with a marked increase in hypoglycemic events and related morbidity⁷.

As a result of these findings, HbA1c has become the “gold standard” for monitoring the degree of glycemic control and thus is used for estimating the risk of complications. For this reason both the American Diabetes Association (ADA) and the American College of Endocrinology (ACE) have issued recommendations detailing targets for glycemic control based on HbA1c level in an attempt to minimize complications without excessive development of hypoglycemia related problems^{8,9}. The ADA has suggested a target HbA1c of 7.0% (about the average HbA1c reached in the DCCT trial with intensive therapy). The ACE recommendations are more stringent and suggest a near normal target of HbA1c of < 6.5%. For both ADA and ACE recommendations, the goal of HbA1c reduction is tempered by the potential for development or worsening of hypoglycemic events due to an attempt at tight control. Therefore, consideration of both glycemic control by HbA1c and potentially morbid hypoglycemic events must be gauged in parallel to glean a full assessment of optimal care of the diabetic patient.

At present, the only therapeutic option to restore entirely normal glucose homeostasis requires β cell replacement by transplantation. To date, whole organ pancreas transplantation has been the primary method of β cell replacement used for Type 1 diabetic patients and has proven highly efficacious in normalizing glucose control¹⁰⁻¹². Considerable evidence suggests that successful pancreas transplantation can retard the progression, and in some cases reverse some of the long-term complications, of the disease including nephropathy and neuropathy¹³⁻¹⁷.

Despite this evidence, the procedure is considered appropriate for only a few diabetics because of its highly invasive nature and the potential for significant morbidity and life-threatening complications. In fact, a recent database analysis questioned the survival benefit of pancreas transplantation in the setting of pancreas alone (PTA) transplants and in pancreas after kidney (PAK) transplants^{18,19}. However, a marked survival benefit was evident for those patients receiving a combined kidney-pancreas transplant (though the relative benefit of the kidney versus the pancreas has not been differentiated). While these data remain both unconfirmed and controversial, at a minimum they suggest a narrow therapeutic margin for the whole organ pancreas transplant procedures in terms of overall survival benefits. Similar conclusions were supported by a recent analysis by Grussner²⁰ in

response to the report of Venstrom et al¹⁸. Their analysis challenged the assertion that PAK or PTA was accompanied by a survival disadvantage, but they were unable to find evidence for a clear survival advantage conferred by the procedures. Quality of life (QOL) from being rendered insulin independent was not considered in either study and is an important weakness in these investigations.

Interest in replacement of the β cell mass by a less invasive means using isolated islets has been piqued by the report from investigators from Edmonton in 2000²¹. Their results suggested for the first time that diabetes could be consistently reversed by transplantation of isolated islets.

In the four years since this landmark report, nearly 500 islet transplants have been performed by more than 40 centers worldwide²². Although the results have been variable depending on the experience of the transplanting center, at the most experienced sites, reversal of hyperglycemia has been routinely achieved²³⁻²⁸. The success of islet transplantation in the prior decade provided the foundation for seeking FDA approval for islets as a standard of care cellular therapy for Type I diabetic patients with labile disease manifest by either poor control on optimal therapy or with life threatening hypoglycemia. Phase 3 trials currently being conducted by the Clinical islet transplant consortium CIT are in their final phases, and have the potential to secure FDA approval of islets as a standard therapy in the near future.

In these trials and others, success is highly dependent on securing a sufficient engrafted islet mass to sustain long term normoglycemia. Improvements in donor selection along with better standardization of islet manufacturing now allow a high degree of assurance that a selected donor pancreas will yield a transplantable preparation of islets. The successful infusion rate of islets has been consistently 40-50% in the Edmonton protocol era and about the same in the CIT trial. With this background, our focus has shifted to improving the fate of islets early after transplantation *in vivo* with the expectation that this will also improve the long term durability of function.

Loss of Islet Mass in the Peritransplant Period

Davalli et al first reported in a quantitative manner that the majority of transplanted islets are lost almost immediately post-transplant²⁹. This occurs in both the autograft and allograft setting and in both renal subcapsular and intraportal sites. The mechanisms of early islet loss are not fully understood but inflammatory, coagulation, and complement pathways have been implicated in the process which has been recently termed, an immediate blood islet inflammatory response (IBMIR)³⁰. IBMIR has been monitored by detection of thrombin-anti-thrombin complexes (TAT) and C3 levels which rise abruptly during the first hour after the islet infusion. Early islet damage has also been detected with imaging studies and the extent of islet loss is as high as 70-90% in some studies^{29, 31-32}.

Experimental therapies successful at preventing early islet loss have helped to define the key mediators and pathways involved, even though not all are easily targeted clinically. Embolization of isolated islets into the portal system sets up the unnatural condition of a damaged tissue being placed directly into intravascular space³³. In mice, islet infusion into the liver leads to occlusion of terminal portal venules and causes areas of hepatic ischemia and infarction³⁴ and in humans a rise in LFTs signifying hepatocyte injury and may suggest events similar to those in mice³⁵. Local stagnation of portal blood further reduces the oxygen tension of an already hypoxic environment, thereby exacerbating islet and surrounding liver ischemia and injury³⁵. Islet and liver injury along with inflammatory mediators expressed by islets post isolation injury (tissue factor, monocyte chemoattractant protein-1 (MCP-1) and C5 receptor)³⁶ and/or surrounding ischemic liver associated danger signals lead to innate immune system activation and to triggering coagulation, activation of platelets and complement³⁷. Down regulation of tissue factor improves engraftment³⁸⁻³⁹, as does a complement inhibitor specifically targeting C5⁴⁰⁻⁴¹, a potent inflammatory stimulus. Toll receptor triggering on islets appears to be a pivotal innate signal as TLR4-TLR2 deficient islets fare better⁴² and survival is improved by targeting a natural ligand for TLR2 and TLR4, HMGB1, a key alarmin secreted by injured islets⁴³.

A variety of anticoagulation approaches, LMW-dextran⁴⁴, islet surface heparinization⁴⁵, Activated

protein C⁴⁶, thrombomodulin⁴⁷⁻⁴⁸, and islet coating with PEG-urokinase⁴⁹ have all been found to increase engrafted mass. Neutralization of potent inflammatory cytokines such as TNF α and IL-1 has also proven beneficial in experimental islet models⁵⁰⁻⁵¹; as a result, blockade of TNF α signaling with a fusion protein of soluble TNFr-Fc (Etanercept) has become standard in clinical islet transplantation⁵²⁻⁵⁴ and targeting IL-1 is under intensive clinical study by a number of groups⁵⁵⁻⁵⁶. Some success has also been achieved by targeting more proximal events inciting tissue injury, with free radical scavengers and by attempting to prevent apoptosis of transplanted islets with any of a variety of agents (inhibitors of caspases⁵⁷, JNK⁵⁸, XIAP⁵⁹, and IKK-beta⁶⁰, and A20 expression)⁶¹.

Alpha-1 antitrypsin (AAT), a 52 Kd glycoprotein acute phase reactant and serum serine protease inhibitor that is released during injury and inflammation⁶². It is the most abundant proteinase in the serum with normal levels of 1.5-3.5 ng/ml that increase ~twofold with inflammation. A number of human serum derived AAT preparations are approved for use in patients with functional AAT deficiency⁶³. AAT exhibits diverse anti-inflammatory properties by blocking inflammatory mediators such as IL-1, IL-6, IL-8 and TNF α and leads to increases in natural anti-inflammatory proteins IL-10 and IL-1rA and may block complement activation and DC maturation. In vitro, AAT has demonstrated cytoprotective effects on islets⁶⁴. Interest in applying AAT to promote islet graft survival was spurred by studies by Dinarello showing that AAT treatment prolonged mouse islet allograft survival⁶⁵⁻⁶⁶. The benefit of AAT was limited by rapid development of mouse anti-human AAT (hAAT) antibodies that defeated the activity of AAT. In subsequent studies, antibody development was avoided using mice tolerant to hAAT by low level hAAT transgene expression. When the immune response to the xeno-protein was eliminated, the beneficial effect of AAT on islet allograft survival was pronounced; in fact, with AAT treatment initiated on d-1 and extending to 14 to 30 days in the absence of any other therapy, not only did allogeneic islet grafts survive long term, but also, donor strain tolerance was achieved⁶⁶. Analysis of tolerant mice found islets to be rich in Tregs and to contain high levels of TGF- β , IL-10, and IL-1 but low expression of inflammatory mediators by RT-PCR. There was also evidence for preserved IL-2 activity in the presence of suppressed inflammation, a setting speculated to be conducive to spontaneous tolerance.

Koulmada et al have recently investigated the molecular basis of the effect of AAT on islet engraftment using a syngeneic islet transplant model⁶⁷. Transplanting a marginal islet mass that reverses diabetes in only 10-25% of untreated mice, the authors found that short-term AAT treatment resulted in normoglycemia in 100% of hosts. Transcriptional profiling of grafts at day 3 and gene autology and the ingenuity pathway analysis found AAT treated grafts to have down-regulated innate immune inflammatory pathways including IL-6, IL-8, IL-10, chemokine signaling, DC maturation and cross-talk between DC and NK cells; key molecular hubs of action included inflammatory molecules TLR, IFN, TNF- α and NF- κ B and chemokines/interleukins.

Also relevant to the application of AAT in clinical islet transplantation is the immunomodulatory effects observed in the context of experimental autoimmune diabetes in NOD mice. When a brief course is administered to recent onset diabetic NOD mice, diabetes is reversed and euglycemia restored in 21 of 24 mice for the duration of the experiment⁶⁸⁻⁶⁹. Moreover, the authors demonstrated that autoimmunity to islets had been eliminated; after rendering treated mice diabetic again (chemically) newly transplanted islet isografts survived without recurrent autoimmunity, providing provocative evidence that AAT treatment allowed self-tolerance to islet autoantigens to be reset.

Also relevant to our proposal is the recent report by Koulmada et al that AAT administration in an NHP islet auto transplant model can dramatically alter the outcome of the graft. In this work, cynomolgus monkeys underwent a 70-80% partial pancreatectomy and the residual islets were ablated with streptozotocin. Islets recovered from the removed segment provided a marginal mass for transplantation of only 1600-4100 IEq/Kg. In untreated controls, islet function was gradually lost at 3-6 months post transplant by non-immunological causes (perhaps exhaustion) with glycemic instability and falling c-peptide levels. In contrast, recipients treated similarly but who received AAT 60 mg/kg on d-1,3,7 and 14 manifest normoglycemia for >700-1200 days with none reverting to hyperglycemia. The transcriptional signature of treated versus controls at the time function was being lost in the controls

was also informative. Using pathway and gene network analysis, critical hubs of interest included NFkB, AKT and TGFb.⁷⁰

With these data as a foundation, a number of trials have been initiated treating new-onset diabetics with AAT in an attempt to ameliorate the accompanying inflammatory lesion and potentially reestablish self-tolerance. The first is a pilot (RETAI Part I) being conducted by our collaborator (co-investigator) on the study proposed herein ([name] with the ITN) who treated 8 pediatric and 8 adult new-onset type I diabetic patients. They used a treatment regimen beginning with a dose of 45 mg/kg dosed weekly for 6 weeks, followed by a 3-week washout period and then increased the dose to 90 mg/kg/week for 6 weeks (for a total of 12 weekly infusions). Potentially important in the design of the trial is the analysis by the ITN mechanistic core, which revealed that inhibition of inflammatory cytokines and modulation of NFkB and apoptotic pathway genes occurred at blood levels that were attained with the 90 mg/kg dose but not the 45 mg/kg dose; moreover, the 90 mg/kg dose was safely administered without any serious AEs. Metabolic data at 12 months (stimulated C-peptide secretion, insulin use, and HbA1c) are stable and show preservation of C-peptide responses at 1 year relative to baseline. Based on further analysis of mechanistic and PK data, they concluded that a dose in the range of 90-180 mg/kg/week will be optimal in terms of the plasma concentrations attained and the duration of drug levels above the threshold for 50% inhibition of cytokine and NFkB responses.

Gottlieb et al studied AAT treatment in a phase I open label trial in 12 recent onset Type I diabetic patients treated with 8 consecutive weekly infusions of 80 mg/kg. That 5 of the 12 patients manifest sustained c-peptide responses at 12 ad 18 months was viewed as encouraging data. In addition, mechanistic analyses revealed reduced levels of TLR induced IL-1b expression in monocytes and DCs at 12 months post AAT treatment⁷¹.

Also noteworthy is that there are two corporate-sponsored trials of AAT in new-onset T1D that have recently started recruiting including: one study sponsored by Grifols Therapeutics Inc., which the investigators will explore doses up to 180 mg/kg/week (NCT02093221) and the second by Kamada Ltd., which will explore doses up to 120 mg/kg/week (NCT02005848).

A more recent analysis studied AAT treated bone marrow transplant recipients with steroid refractory GVHD, Marcondes et al utilized a modified every other day regimen of AAT (GLASSIA) that achieved stable serum AAT levels in the desired target range⁷². Their regimen consisted of a 90 mg/kg load followed by 60 mg/kg every other day for 8 doses. We have adopted a modified version of this regimen for our trial that contains a total weekly dose in the Grifols trial of 120 mg/kg/wk.

Based on the above findings, we contend that the diverse inflammation targeting properties of AAT may simultaneously impact critical impediments to islet transplantation – alloimmunity, autoimmunity, and innate/inflammation induced early post-transplant islet loss. Given that in addition to the study patients noted above, AAT has been administered safely long term to large numbers of patients as replacement therapy in the setting of AAT deficiency⁷³⁻⁷⁴, and has proven highly safe even in immunosuppressed post-lung transplant patients, in conjunction with the fact that it is readily commercially available, makes the agent an exciting therapy to improve islet transplant success.

In the current trial, we will capitalize on data from the CIT-06 trial (with permission of the CIT steering committee) that has completed enrollment of 24 IAK patients and has now passed the 1 year primary endpoint. Since the proposed cohort to be treated with AAT is otherwise similar in terms of recipient selection, islet manufacturing, medical management and post transplant follow-up, we will have a large carefully studies control cohort that will maximize trial efficiency and power to detect meaningful increases in islet mass manifest by single donor insulin independence rates at day 75. Since the day 75 single donor insulin independence rate in CIT-06 was relatively low (and nearly identical to the IAK experience in the CITR registry) at 17%, meaningful increases in engrafted mass gained by AAT therapy should be readily detectable in our study.

Use of an auxiliary islet graft in the subcutaneous tissue to monitor islet histopathology

